6.2.3 Other secondary endpoints

- SARS-CoV-2 specific T- and B- cell responses⁵
- High sensitivity SARS-CoV-2 antibody titer (IgM, IgE, IgA, IgG1, IgG2, IgG3, IgG4)
- Changes in host gene and protein expression from matched blood and respiratory (NP) samples at the single cell level (B, T, natural killer, and myeloid cells).
- Changes in T- and B-cell receptor (TCR/BCR) repertoire from matched blood and respiratory (nasal/oropharyngeal) samples.
- Pyroptosis (aberrant proinflammatory cell death) assays.⁶

6.2.4 Analysis of AE data

Analysis of AE data will primarily be descriptive based on MedDRA coding of events. Rates of AE will be compared between randomized arms using Fisher's Exact Test.

6.2.5 Analysis of plasma inflammatory biomarkers and SARS-CoV-2 antibody levels

Analysis of titers will primarily be descriptive, comparing the geometric mean titers at days 0, 1, 5, 15, and 31 between the randomized arms. Furthermore, it is of interest to describe the entire distributions of plasma inflammatory cytokine levels or anti-SARS-CoV-2 antibody titers by randomized arms and contrast these distributions. Therefore, we will use quantile regression in order to describe whether there is a shift or change in the titer distribution between randomized arms. Given that repeated measures of titers will be obtained, we will account for the correlation in measures within individuals using a cluster bootstrap in order to properly estimate the p-value and 95% confidence intervals. Similar analysis will also be applied to lymphocyte counts on days 0, 1, 5, 15, and 31, hematological measurements (D-dimer, ferritin, LDH, hsCRP) on days 0, 1, 5, 15, and 31, and other lab measures showing right-skewed distributions

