5.3.2 Exclusion Criteria

1. Pregnant, breastfeeding, or unwilling to practice birth control during participation in the study
2. Active malignancy requiring systemic chemotherapy or surgery in the preceding 3 months or for whom such therapies are expected in the subsequent 6 months
3. Decompensated liver disease as defined by the presence of ascites, encephalopathy, esophageal or gastric varices, or persistent jaundice
4. Serious illness requiring systemic treatment and/or hospitalization in the 3 months prior to study enrollment
5. Concurrent treatment with immunomodulatory drugs, and/or exposure to any immunomodulatory drug in the 4 weeks prior to study enrollment (e.g. corticosteroid therapy equal to or exceeding a dose of 15 mg/day of prednisone for more than 10 days, IL-2, interferon-alpha, methotrexate, cancer chemotherapy). NOTE: use of inhaled or nasal steroid is not exclusionary.
6. Serious medical or psychiatric illness that, in the opinion of the site investigator, would interfere with the ability to adhere to study requirements or to give informed consent.
7. Current alcohol use disorder or hazardous alcohol use (>7 drinks per week for women or > 14 drinks per week for men) as determined by clinical evaluation.
8. Current use of any drug formulation that contains alcohol or that might contain alcohol
9. Current use of warfarin.
10. Current use of oral lopinavir/ritonavir solution (and the inability to switch to a solid dosage form during the entire duration of the study).
11. ALT or AST > 2 x the upper limit of normal or total bilirubin outside the normal range.
12. Creatinine clearance (CrCl) < 50 mL/min by Cockcroft-Gault)
13. Allergy to rubber or thiuram derivatives

Note: Receipt of medications with potential anti-COVID activity that are considered standard-of-care at the study site (e.g., small molecules or monoclonal antibodies directed against SARS-CoV-2) is permitted during the trial. Prior receipt of current standard of care inpatient COVID-19 treatment, including remdesivir, convalescent plasma/sera, and dexamethasone,¹¹⁷ is also permitted and should be recorded as a prior medication.

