5.3.8 Prohibited medications

For study days 1-31, use of medications that are considered standard-of-care at the study site (including antiviral medications available under Emergency Use Authorization) is permitted. Use of other medications with potential anti-SARS-CoV-2 activity, including off-label, expanded access, or investigational agents, should be discussed with the team.

Note: Participants who are hospitalized during the study are eligible to receive COVID-19 treatment per local standard of care, including remdesivir, immunomodulatory agents and/or convalescent sera/plasma and will not be excluded from the study if receiving this standard of care. Azithromycin administered for treatment of presumed or confirmed infection will be permitted.

After study day 31, use of anti-COVID-19 treatments as salvage therapy for those with persistent severe COVID-19 are permitted but should be recorded.

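### Section 6.2.5 compares SARS-CoV-2 antibody titers by arm with no rule for values taken after permitted monoclonal antibodies or convalescent plasma, so recipients' titers mix passive with host antibody

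*Combined protocol and SAP*

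**What the plan says.** Section 6.2.3 lists among the other secondary endpoints "High sensitivity SARS-CoV-2 antibody titer (IgM, IgE, IgA, IgG1, IgG2, IgG3, IgG4"). Section 6.2.5 opens by giving the status of the analysis: "Analysis of titers will primarily be descriptive". It then specifies "comparing the geometric mean titers at days 0, 1, 5, 15, and 31 between the randomized arms", and adds "we will use quantile regression in order to describe whether there is a shift or change in the titer distribution between randomized arms", with a cluster bootstrap for p-values and 95% confidence intervals. Section 6.2 puts all main analyses on an intention-to-treat basis.

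Three provisions allow antibody products:

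- **Monoclonal antibodies on study.** The note to section 5.3.2 says that receipt of site standard-of-care agents such as "small molecules or monoclonal antibodies directed against SARS-CoV-2) is permitted during the trial".
- **Convalescent plasma before entry.** The same note permits and asks to have recorded "Prior receipt of current standard of care inpatient COVID-19 treatment, including remdesivir, convalescent plasma/sera, and dexamethasone".
- **Convalescent plasma on study.** Under section 5.3.8, participants hospitalized during the study may receive local standard of care, "including remdesivir, immunomodulatory agents and/or convalescent sera/plasma and will not be excluded from the study".

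Prior receipt of such inpatient treatment is to be recorded as a prior medication (5.3.2), and concomitant medications go on the CRF to day 31 (5.3.7). Section 6.2 does not link either record to the titer analysis.

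**The concern.** The schedule of evaluations in section 5.4 says that the frequent sampling is meant to capture drug levels and the human immune response. A reader will take a difference in antibody titer between arms as a difference in host response. A titer drawn after a monoclonal antibody or convalescent plasma may contain antibody that the participant did not make. If such values enter the comparison unmarked, a ratio of geometric means, or a shift in the upper quantiles, can reflect who received a product.

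Each cohort has 20 active and 10 placebo participants, so very few recipients are needed to move an arm summary. In-trial plasma follows hospitalization, and hospitalization is itself a secondary outcome that the drug is hoped to change. Receipt after randomization could therefore depend on the arm, which would be bias and not only noise.

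**Working it through.** **Step 1. Is there a rule elsewhere?** These are the places where one could sit:

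- Section 6.2 names risk stratum and pre-treatment RNA as adjustments, but only for detectable viral RNA.
- Section 6.2 mentions interactions with other therapy, but only as a candidate covariate in the pharmacokinetic model.
- The missing-data text in 6.2 covers missing covariates and imputation. A titer taken after a product is not missing.
- Section 6.2 ranks participants whose diaries are incomplete because of hospitalization or death as having poorer outcomes. A post-randomization event is thus handled for symptoms but not for titers.
- Section 6.2.5 has no exclusion, flag, stratification or adjustment for antibody products. It names no assay target that would separate product from host antibody.

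The gap is confirmed.

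**Step 2. Is there a figure to reproduce?** No. The only power statement (6.1) concerns IL-6. The documents give no titer SD, no target difference, no rate of product use and no effect of a product on measured titer. Everything below rests on assumed values, shown as ranges.

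**Step 3. Shift in an arm's geometric mean.** Let a share f of an arm carry a rise of D log10 from the product. The arm's geometric mean is multiplied by 10^(f×D).

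| Recipients | f | D = 1 (10-fold) | D = 2 (100-fold) | D = 3 (1000-fold) |
|---|---|---|---|---|
| 1 of 10 placebo | 0.10 | 1.26 | 1.58 | 2.00 |
| 1 of 20 active | 0.05 | 1.12 | 1.26 | 1.41 |

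If the shares are equal (2 of 20 and 1 of 10), both arms move by 10^(0.1×D) and the ratio between arms is unchanged. Only a difference in share shifts the contrast.

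**Step 4. Chance difference in share.** With expected use p in both arms, the SD of the difference is sqrt(p(1−p)(1/20 + 1/10)). One SD of imbalance multiplies the ratio between arms by 10^(SD×D).

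- p = 0.20: sqrt(0.16 × 0.15) = 0.155, giving 1.4, 2.0 or 2.9 for D = 1, 2, 3.
- p = 0.05: sqrt(0.0475 × 0.15) = 0.084, giving 1.2, 1.5 or 1.8.

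**Step 5. The same variation seen as lost precision.** This is another view of step 4 and must not be added to it. The log10 SD becomes sqrt(s² + f(1−f)D²), where s is the host SD. Take f = 0.10 and D = 2, with power for a 3-fold difference, 20 v 10, two-sided 0.05:

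- s = 0.4: sqrt(0.16 + 0.36) = 0.72, and power falls from 87% to 40%.
- s = 0.6: sqrt(0.36 + 0.36) = 0.85, and power falls from 54% to 31%.

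**Step 6. Against ordinary sampling error.** With no product use, the 95% margin on the ratio is 10^(1.96 × s × sqrt(0.15)). That is 2.0-fold for s = 0.4 and 2.9-fold for s = 0.6. A single placebo recipient (step 3) stays within that margin for 10- or 100-fold rises and about reaches the smaller margin at 1000-fold.

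**The case against.** The strongest reply is that this is a secondary, primarily descriptive comparison in a study that section 6.2 calls exploratory. Chance imbalance in permitted care is random error that the bootstrap intervals already reflect. Step 6 adds that one recipient seldom moves the ratio beyond ordinary noise. All of this stands and limits the weight of the point. It does not answer receipt that depends on the arm, and it does not make the planned p-values and intervals interpretable as host response.

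Four stronger readings are tempting, and the documents do not support them:

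- **That both kinds of product are expressly allowed before entry and throughout.** Monoclonal antibodies are named only during the trial; prior use is not excluded, but it is not named either. In-trial plasma is named only for participants hospitalized on study. Prior inpatient plasma should be uncommon, because exclusion 4 bars serious illness requiring systemic treatment and/or hospitalization in the previous 3 months. That criterion is in tension with the note in the same section, and the two must be reconciled.
- **That the endpoint measures passive antibody in place of host response.** Only recipients are affected, only after receipt, and only in the classes and targets present in the product. Seven classes and subclasses are listed, and no assay target is given, so the documents do not show which would register a given product.
- **That a particular distortion can be quoted.** The rates and fold rises in the working are assumptions.
- **That post-receipt titers should simply be dropped from the main analysis.** In-trial plasma follows hospitalization, so dropping those values would remove sicker participants, possibly unequally by arm, and would depart from the intention-to-treat rule in 6.2.

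**Conclusion.** The point holds in limited form. Followed as written, section 6.2.5 would pool titers taken before and after permitted antibody products, and its comparison between arms could not be read cleanly as host antibody response. The on-study monoclonal provision is enough by itself to sustain this. Receipt that is equal between arms mainly costs precision; receipt that differs by arm shifts the contrast. The illustrative size is the one-recipient placebo row in step 3 of the working. It rests on an assumed 10- to 1000-fold rise, on one recipient in ten, and on an assay that detects the product. No size follows from the documents. The point is confined to the antibody titers and is worth correcting because the remedy is cheap and should be settled before unblinding.

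**What to change.** Add to section 6.2.5 wording to this effect:

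> Receipt of any anti-SARS-CoV-2 monoclonal antibody or convalescent plasma/sera will be flagged by date from the recorded prior and concomitant medications and tabulated by randomized arm and dosing cohort. The intention-to-treat comparison of titers will use all values. Alongside it, the geometric mean and quantile regression analyses will be repeated with titers taken after receipt set aside, including all titers from participants with receipt before Day 1. Conclusions about host antibody response will be drawn only when both analyses are read together.

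Confirm that the CRF captures the administration date, since the documents say only that these medications are recorded. Separately, reconcile exclusion 4 with the note in section 5.3.2 on prior inpatient treatment, so that it is clear whether pre-entry plasma can occur.

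The cost is SAP text and one extra set of tables, with no new visit or sample. The downside is that some titers are lost from the restricted analysis, and the remaining set may be selected if receipt differs by arm. For that reason the restricted analysis accompanies the comparison of all values and does not replace it, and the receipt table should be shown with both.

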5.4 Study procedures

5.4.1. Figure 1. SCHEDULE OF EVALUATIONS:

	Screen/ Baseline	Day 1 Clinic	Day 2 Clinic	Day 3 Phone	Day 4 Phone	Day 5 Pre dose	Day 5 2-hour Post dose	Day 5 4-hour Post dose	Day 7 Phone	Day 9 Phone	Day 15 Clinic	Day 31 Clinic
Informed Consent	X											
Release of information	X											
Questionnaire		X					X				X	X
Symptom diary/ AE check	X	X	X	X	X		X		X	X	X	X
Vital signs (BP, HR, R, Temp, SP02)	X	X ^a				X ^a	X ^b	X ^b			X	X
Targeted Physical Exam	X	X				X					X	X
SARS-COV-2 PCR TEST	X											
Saliva		X				X ^a					X	X
Complete blood count with differential	X		X ^b			X ^a					X	X
Comprehensive Metabolic Panel	X		X ^b			X ^a					X	X
Erythrocyte Sedimentation Rate (ESR)	X		X ^b			X ^a					X	X
C-Reactive Protein (Inflammation)	X		X ^b			X ^a					X	X
D-Dimer	X		X ^b			X ^a					X	X
Lactate Dehydrogenase (LDH)	X		X ^b			X ^a					X	X

Ferritin	X		X ^b			X ^a					X	X
Urine Pregnancy test (if WOCBP)	X					X ^a						
CD4+/CD8+ T cell counts (if HIV positive)	X											X
HIV RNA-standard Assay (if HIV positive)	X											X
PK Samples			X ^b			X ^a	X ^b	X ^b			X	X
PBMC		X				X ^a	X ^b	X ^b			X	X
Plasma		X				X ^a	X ^b	X ^b			X	X
Serum		X				X ^a	X ^b	X ^b			X	X
NP Swab		X	X ^b			X ^a					X	X
Study Drug/Placebo Administration (Given after blood collection on clinic visit days)		X	X	X	X	X						
• Cohort 1 = (N=20) 1000mg/day; (N=10 placebo)												
• Cohort 2 = (N=20) 2000mg/day; (N=10 placebo)												

a=predose

b=post-dose

The frequent time points are to detect both drug levels and human immune response. Red Cross limits are 500 mL per two months, which we do not exceed in this study. There is no stated guideline for blood volumes for this patient population, so we are utilizing the guidelines from interventional HIV cure trials, when often, serial blood sampling are completed in a single day. The total volume collected at each visit is as follows:

Day 0 Screen/Baseline:	15 mL
Day 1: Pre-Dose	65 mL
Day 2: Post Dose	19 mL
Day 5 Hour -0.5 pre-dose:	59 mL
Day 5 Hour 2 post dose:	45 mL
Day 5 Hour 4 post dose:	45 mL
Day 15:	79 mL
Day 31:	79 mL

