5.5.2 Study Drug/ Placebo Administration (Day 1)

5.5.2.1 Pre-Dose (Between Hour -0.5 and 0)

1. Questionnaire Evaluation to include the Index Follow up Questionnaire
2. Targeted physical exam and vital signs
3. Clinical lab collection

4. Samples collected for research (storage)
 - a. Blood: PBMC (CyTOF, single cell sequencing), plasma (plasma SARS-CoV-2 viral load), serum (SARS-CoV-2 serology)
 - b. Nasopharyngeal swab for SARS-CoV-2 viral load
 - c. Saliva for host DNA sequencing and potential future SARS-CoV-2 quantification (RNA levels and anti-SARS-CoV-2 IgA)

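### Section 6.2.5 lists pre-dose days among the days compared between arms and leaves open both the days pooled in the quantile regression and the use of the baseline value

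*Combined protocol and SAP*

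**What the plan says.** Section 6.2.5 covers plasma inflammatory biomarkers and antibody levels. It opens with "Analysis of titers will primarily be descriptive" and describes this as "comparing the geometric mean titers at days 0, 1, 5, 15, and 31 between the randomized arms". For the whole distribution, "we will use quantile regression in order to describe whether there is a shift or change in the titer distribution between randomized arms". Because each person contributes several values, the plan will "account for the correlation in measures within individuals using a cluster bootstrap in order to properly estimate the p-value and 95% confidence intervals". It then extends the approach: "Similar analysis will also be applied to lymphocyte counts on days 0, 1, 5, 15, and 31", and to D-dimer, ferritin, LDH and hsCRP on the same days.

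The regression is given no list of days of its own, no visit or arm-by-visit term, and no covariate.

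On timing, the blood-volume list in section 5.4 has "Day 0 Screen/Baseline" and labels the Day 1 draw as pre-dose. Section 5.5.2.1 places the Day 1 research samples before hour 0: "Blood: PBMC (CyTOF, single cell sequencing), plasma (plasma SARS-CoV-2 viral load), serum (SARS-CoV-2 serology").

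Elsewhere, section 6.1 adjusts the mixed-model analysis for pre-treatment cytokine level. Section 6.2 compares biomarkers by Wilcoxon tests, naming days 5 and 15 as examples, and adjusts detectable SARS-CoV-2 RNA for its pre-treatment level. Section 6.2.1 defines the primary endpoint as change at days 5, 15 and 31.

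**The concern.** Before the first dose, randomization makes the arms equal in expectation. A comparison on days 0 and 1 therefore measures only chance imbalance. The pre-dose value is useful as a covariate, because it explains part of the between-person spread on later days.

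Section 6.2.5 does not assign it that role. It names days 0 and 1 next to the post-dose days and then describes one shift between arms, with no day attached. An analyst could follow the section exactly and fit a single arm effect to all listed days, averaging the post-dose effect with days on which the effect is zero. Another analyst could fit arm-by-day terms and avoid this, but would still have no instruction to use the baseline. The adjustment in section 6.1 is tied to the mixed model and to cytokines, so it does not reach antibodies or laboratory measures.

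At stake is the size and precision of the distributional contrasts for cytokines, antibodies, lymphocytes and inflammatory laboratory values, for which p-values and intervals are planned.

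**Working it through.** **The plan's own power figure.** Section 6.2.5 states no effect or power. Section 6.1 states about 80% power for a 35% difference, mean IL-6 36.7 pg/mL, SD 12 (printed as ng/mL, read here as pg/mL), alpha 0.05, and 20 v 10 per cohort.

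- Difference: 0.35 × 36.7 = 12.845, or 12.845/12 = 1.07 SD.
- SE: 12 × √(1/20 + 1/10) = 4.648.
- Two-sided power: Φ(12.845/4.648 − 1.96) = Φ(0.80) = 79%.

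The figure reproduces. It belongs to section 6.1 and serves here only as a scale.

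**Pre-dose values per measure.** The schedule in section 5.4 marks research plasma and serum at Day 1 and not at screening, so cytokines and antibodies have one pre-dose value. For clinical laboratory measures it marks screening and not Day 1, but section 5.5.2.1 lists an unspecified clinical laboratory collection on Day 1. Those measures have one pre-dose value by the table, and possibly two.

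**Dilution under one common arm effect.** With k pre-dose and 3 post-dose days, equal weights and a constant post-dose effect, the estimated shift is 3/(3+k) of the true one.

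- k = 1: 3/4, diluted by 25%.
- k = 2: 3/5, diluted by 40%.
- One pre-dose draw, with all three Day 5 plasma/serum draws counted separately: 5/6, diluted by about 17%.
- Per-day comparison or arm-by-day terms: 0%.

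A simulation of arm-only median regression with a participant-level bootstrap (20 v 10, 400 trials per setting, true shift 1.07 SD) gave pooled estimates of 0.83 to 0.84 with one pre-dose day (about 22% low) and 0.64 to 0.67 with two (37% to 40% low).

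**Precision.** The documents give no within-person correlation ρ, so 0.3, 0.5 and 0.7 are assumed, equal between all days. For a unit-variance log outcome and one pre-dose value:

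- post-dose mean, baseline-adjusted: V_adj = (1+2ρ)/3 − ρ²
- post-dose mean, unadjusted: V_post = (1+2ρ)/3
- mean of all four days: V_pool = (1+3ρ)/4, with effect × 0.75

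Set the effect so that the adjusted analysis has 80% power (z = 1.960 + 0.842 = 2.802). Power of each alternative is Φ(2.802·r − 1.96), with r_post = √(V_adj/V_post) and r_pool = 0.75·√(V_adj/V_pool).

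| ρ | V_adj | V_post | V_pool | r_post | Power, post-dose unadjusted | r_pool | Power, pooled |
|---|---|---|---|---|---|---|---|
| 0.3 | 0.443 | 0.533 | 0.475 | 0.912 | 72% | 0.725 | 53% |
| 0.5 | 0.417 | 0.667 | 0.625 | 0.791 | 60% | 0.612 | 40% |
| 0.7 | 0.310 | 0.800 | 0.775 | 0.622 | 41% | 0.474 | 26% |

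At the section 6.1 effect of 1.07 SD, 20 v 10, one pre-dose day and the same three correlations, power is 98.6%, 99.0% and 99.9% adjusted; 96.6%, 92.3% and 87.1% post-dose unadjusted; and 85.3%, 74.6% and 65.3% pooled. The relative loss from pooling, against the adjusted analysis, is 14% to 35%.

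The adjusted figures treat the baseline slope as known; estimating it costs a little.

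**False positives.** With no true effect, two pre-dose days and ρ = 0.5, the pooled test rejected in 6.1% of 1,000 simulated trials, close to the nominal 5%.

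**The case against.** The strongest reply is that the text does not say the pre-dose days are pooled. The geometric-mean sentence is introduced as descriptive and reads most naturally as one comparison per day, where days 0 and 1 dilute nothing. The quantile-regression sentence names no days and no single arm effect. A cluster bootstrap is needed just as much with arm-by-day terms, so it is not evidence of pooling. This stands: pooling is a possible reading of an under-specified model.

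A reader might go further and infer that section 6.2.5 dilutes the effect by up to 40% and roughly halves power. The documents do not support that. For cytokines and antibodies the schedule provides one pre-dose draw. The power loss depends on a correlation that the plan does not give and on the chosen effect size; at the effect in section 6.1 with one pre-dose day it is 14% to 35%.

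The constant-effect assumption is also open to challenge, since dosing lasts five days and section 4.1.6 gives a half-life of 7.3 hours. For means, (0 + d5 + d15 + d31)/4 is still three quarters of the post-dose average, but not of the Day 5 effect. If the effect existed only on Day 5, four pooled days would show a quarter of it and three post-dose days a third. So removing the pre-dose days is not enough without arm-by-day terms.

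Finally, a baseline covariate makes quantile regression estimate conditional quantiles. These can differ from the shift in the marginal distribution that the section wants to describe, unless the effect is a pure location shift. This is a small but real cost of the change.

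The objection does not explain why the baseline has no stated role in a section that plans p-values and intervals.

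**Conclusion.** The point holds as a gap in specification that should be closed, and its size depends on the model eventually fitted. With one common arm effect over the listed days, attenuation is about 25% for one pre-dose value per measure, about 17% if every Day 5 plasma/serum draw counts, and 40% only where two pre-dose values exist. This rests on equal day weights and a constant post-dose effect. With per-day or arm-by-day contrasts the attenuation is zero and the loss is the precision of a baseline already collected, as in the unadjusted column of the table, under equal correlation between days.

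A reader might also infer that the primary analysis is compromised. It is not: the mixed model in section 6.1 and the GEE and Wilcoxon comparisons in section 6.2 do not use this contrast. The harm is understated or imprecise contrasts in a largely descriptive section, without excess false positives.

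**What to change.** In section 6.2.5:

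- State that the outcome days for the geometric-mean and quantile-regression contrasts are 5, 15 and 31, with arm-by-day terms.
- Enter each participant's last pre-dose log value as a covariate in both contrasts, for cytokines, antibodies and laboratory measures alike. Name the visit that supplies it for each measure.
- Show days 0 and 1 descriptively, without an arm test.
- Present the unadjusted post-dose distributions by arm beside the adjusted quantile contrasts, so that the marginal description is kept.
- State whether the three Day 5 draws count as one day or as separate values.

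The cost is SAP wording, one covariate per model and one additional display. No new data are needed. The choice should be fixed before unblinding.
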